## **Introduction**

The application of standard evidence-based prevention interventions can decrease the incidence of pressure injuries (PIs). However, the development of serious PIs in high-risk patients in the early postoperative period remains a significant clinical challenge. Following surgery, PIs that appear within 1 to 5 days are often deep-tissue pressure injuries (DTPIs) [1].

The etiology of DTPIs remains a topic of ongoing discussion among experts, and a comprehensive understanding of the underlying pathophysiological mechanisms has yet to be achieved. One commonly accepted hypothesis posits that the occurrence of DTPIs can be attributed to the application of pressure or shear stresses, or a combination thereof, resulting in cellular deformation and eventual necrosis. The DTPIs exhibit a distinctive complexity due to the co-occurrence of ischemia and mechanical stress, thereby expediting the consequent harm [2,3]

[figure not shown]
- 1 -

Title: Effectiveness of polyurethane foam (pink pad) compared with Mepilex dressing for pressure ulcer prevention in operating room

Version: 2.0 (20-Jun-2023)

Effective date: 15-Aug-2023

Expiration date: 15-Aug-2024

اللجنة المحلية لأخلاقيات البحث  
Institutional Review Board

## **Effectiveness of polyurethane foam dressing compared with Mepilex dressing for pressure ulcer prevention in operating room: A randomized control clinical trial.**

DTPIs exhibit a discernible pattern of evolution. Initially, the affected area manifests abruptly as intact skin that exhibits discoloration, either in the form of purple or hyperpigmentation [2]. The lesions evolve into slender vesicles atop a dusky ulceration site, transforming into black eschar. Subsequently, the DTPI becomes unsealed, exposing a pressure injury that has penetrated through the entire thickness of the skin and underlying tissues, indicating a stage 3 or 4 injury [3,4]. According to a study conducted in 2013, it has been observed that wounds of this nature have the potential to heal without any loss of tissue. Nevertheless, it is imperative to provide sustained care and attention to prevent any deterioration [5].

Patients undergoing cardiac surgery are among those at the highest risk of developing PIs, with an incidence as high as 29.5% [6]. Among patients undergoing cardiac surgery, specific risk factors for PI include protracted exposure to pressure during lengthy surgical procedures, vascular disease, and/or postoperative vasopressor use [7]. The high incidence of PI among cardiac surgery patients suggests that conventional methods for preventing PI are inadequate for this population.

There are an increasing number of studies evaluating the efficacy of different dressings (typically multilayer foam dressings) in preventing pressure ulcers (PIs) of the sacrum, heel, and those related to medical devices in ICU and trauma patient populations [8,9]. Recent high-quality randomized controlled trials demonstrated that the use of specialty foam dressings over the sacrum can reduce the incidence of pressure ulcers in intensive care unit (ICU) patients and high-risk nursing home residents [10,11].

Although limited in design and/or sample size, additional research and quality improvement investigations support the efficacy of this intervention in preventing the formation of PIs [12]. The National Pressure Ulcer Advisory Panel, in collaboration with European and Pan-Pacific peer organizations, added a recommendation (with a "B" strength of evidence) to "consider applying a

[figure not shown]
- 2 -

Title: Effectiveness of polyurethane foam (pink pad) compared with Mepilex dressing for pressure ulcer prevention in operating room

Version: 2.0 (20-Jun-2023)

Effective date: 15-Aug-2023

Expiration date: 15-Aug-2024

اللجنة المحلية لأخلاقيات البحث  
Institutional Review Board

## **Effectiveness of polyurethane foam dressing compared with Mepilex dressing for pressure ulcer prevention in operating room: A randomized control clinical trial.**

polyurethane foam to bony prominences (e.g., heels, sacrum) for the prevention of pressure ulcers in anatomical areas frequently subjected to friction and shear" in its 2014 guidelines [13].

The market offers a variety of dressings distinguished by their composition (hydrocolloid, polyurethane foam, etc.), thickness, and dimension. Several in vitro studies compare the ability of the most popular dressings on the market regarding the redistribution of pressure, [15-17] the management of fluids/hydration and the application of friction, which are the primary factors in the onset of PU. In these in vitro investigations, the material that appears to be the most effective overall is polyurethane foam [18], particularly when composed of multiple layers [19]. In two recent clinical investigations involving intensive care unit (ICU) patients, the use of multi-layer foam dressings was found to be an effective method of preventing PU [20].

A systematic review revealed that the prevalence of pressure ulcers among surgical patients increased from 0.3% to 57%. In a study of Brazilian patients undergoing elective surgery, the prevalence of pressure ulcers reached 25 % [21]. 5–53.4% of hospital-acquired pressure ulcers are associated with protracted or multiple surgical procedures, according to studies [22]. In the operating room of a private hospital in western Indonesia, the incidence of pressure ulcers has increased from one case in 2018 to four cases in 2020.

Despite the fact that the data support the use of dressings as a preventative intervention, the reviewers deemed them inconclusive because of the flaws in the study designs, which increased the possibility of bias. Both evaluations recommended further methodologically rigorous research to generate proof of the effectiveness and kind of dressing to use for prevention as their conclusion. King Abdullah medical city has a cardiac center, and a lot of open-heart surgeries are performed there, and both polyurethane foam (pink Pad) and Mepilex dressing are applied to those patients. Therefore, the

## **Effectiveness of polyurethane foam dressing compared with Mepilex dressing for pressure ulcer prevention in operating room: A randomized control clinical trial.**

present study was designed to compare the effects of polyurethane foam (pink Pad) versus Mepilex dressing for prevention of pressure ulcer in operating room.

### **OBJECTIVES:**

The **primary objective** of this study is to:

- To evaluate the efficacy of using polyurethane foam (pink Pad) versus Mepilex dressing in pressure ulcer prevention for patients in operating room.

### **Secondary Objectives**

- Identifying the incidence of post-operative pressure injury for cardiac surgery patients at king Abdullah medical city.

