#### **For the secondary objective**

The occurrence of pressure ulcer will be documented in data collection then calculated.

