### **Inclusion Criteria:**

- Subjects  $\geq 18$ .
- Willing to participate.
- Patients undergoing cardiac surgery.
- Patient who is at risk for PU development as measured with Braden scale.

- 4 -

Title: Effectiveness of polyurethane foam (pink pad) compared with Mepilex dressing for pressure ulcer prevention in operating room

Version: 2.0 (20-Jun-2023)

Effective date: 15-Aug-2023

Expiration date: 15-Aug-2024

اللجنة المحلية لأخلاقيات البحث  
Institutional Review Board

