## **Effectiveness of polyurethane foam dressing compared with Mepilex dressing for pressure ulcer prevention in operating room: A randomized control clinical trial.**

- Patient who has skin intact and having a life expectancy greater than 72 hours as per clinical judgement.

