### **Exclusion Criteria:**

- Subjects under 18
- Not consenting to participate
- Patients with suspected hypersensitivity reactions to any of the dressing formulation's ingredients.
- Patients who are unable to continue the study because of death or change in the care setting.

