## **Effectiveness of polyurethane foam dressing compared with Mepilex dressing for pressure ulcer prevention in operating room: A randomized control clinical trial.**

Prior to surgery, Mepilex Border Sacrum dressings 20 X 20 (Molnlycke Health Care) will be applied to the patient's sacrum for Mepilex Border Sacrum dressings group and polyurethane foam will be used to the patient's sacrum for polyurethane foam group. A nurse in the preoperative patient receiving area will apply the Mepilex Border Sacrum dressings. The perioperative nurse will examine the dressing in the operating room to ensure its integrity. If the perioperative nurse observed any alterations to the original application, such as rolling or displacement, she will reapply it. If the dressing is not applied by the nurse before transferring the patient to the operation room the perioperative nurse will apply it. For polyurethane foam (pink Pad) it will be used only by operating room nurses as it is available only in the operating room. Both types of intervention will be available in the operating room.

Patient will be examined by head nurse of wound management team after the operation then at day 3- and 7-days post operation. The dressing should be removed after 7 days post operation or if there is any clinical indication for removal. If a patient is discharged before 7 days post operation for any reason the head nurse of wound management team will examine the patient before discharge. Follow up will be for maximum 7 days post operation for each subject. Any patient will be unable to continue the study because of death or change in the care setting will be excluded from the study.

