## **Effectiveness of polyurethane foam dressing compared with Mepilex dressing for pressure ulcer prevention in operating room: A randomized control clinical trial.**

the study team to provide an overview of the study's implementation, with the aim of ensuring adherence to quality standards and regulatory requirements. Researchers will explain the study to the participants and take written consent if they want to participate. In cases where a patient is unconscious, written consent will be obtained from their Legally Acceptable Representative in accordance with legal protocols. Voluntary and anonymous participation will be ensured. In case of passing away the collected data will not be used, and safety reports will be submitted as per the local gaudiness. The data collection sheets will be securely stored in a locked file cabinet under the custody of the researchers.

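### Injuries already recorded are discarded when an enrolled patient dies, and on the natural reading when the care setting changes, which can distort both the incidence figure and the randomised comparison

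*Protocol*

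**What the plan says.** **Target.** The Secondary Objectives section gives one item: "Identifying the incidence of post-operative pressure injury for cardiac surgery patients at king Abdullah medical city". Its measure, under Objective measures, is "The occurrence of pressure ulcer will be documented in data collection then calculated". The primary measure in the same section is pressure ulcer incidence in both treatment groups, assessed after the operation and at days 3 and 7.

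**Removal of enrolled patients.** The Exclusion Criteria list "Patients who are unable to continue the study because of death or change in the care setting". The Study Procedure repeats the rule: "Any patient will be unable to continue the study because of death or change in the care setting will be excluded from the study". Section II (Pressure ulcer assessment) says it once more in garbled wording. For deaths, Data Collection and Management goes further: "In case of passing away the collected data will not be used".

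**Early discharge.** The Study Procedure has a separate sentence: "If a patient is discharged before 7 days post operation for any reason the head nurse of wound management team will examine the patient", the examination to take place before discharge.

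**Who is enrolled.** Among the inclusion criteria are consent, cardiac surgery, "Patient who is at risk for PU development as measured with Braden scale" (no cut-off given) and "Patient who has skin intact and having a life expectancy greater than 72 hours as per clinical judgement". The Sample Size calculation section describes a convenience sample of 80, 40 per group, with procedures expected to last over 4 hours. The inclusion and exclusion lists contain no duration condition.

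**The concern.** There are three assessment times, so an injury can be on record before the patient dies or is moved. No section keeps that injury. Followed as written, the plan takes the patient out of both numerator and denominator and reports a percentage among those who remained.

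Two results are at stake. One is the descriptive incidence in the secondary objective. The other, which matters more, is the primary comparison: the removal happens after randomisation, and the Blinding section says that patients, the nurse applying the product and the outcome assessor all know the allocation. Whether a patient is judged unable to continue can then depend on the arm, through the product's effect or through knowledge of it, and the groups left for analysis are no longer the groups that were randomised.

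This cannot simply be left to a statistical analysis plan. An analysis plan that used the data of patients who died would contradict the protocol's own data-use rule. The Exclusion Criteria also list an event that can occur only after enrolment and so cannot be applied at screening.

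**Working it through.** **1. The plan's own figure.** The Sample Size calculation section gives a population of 90, expected frequency 50%, acceptable error 5% and confidence 99%, with a minimum of 79.

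- n0 = z²p(1−p)/d² = 2.576² × 0.25 / 0.0025 = 663.5
- with the finite-population correction, n = 663.5 / (1 + 662.5/90) = 79.4

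The 79 is reproduced. It concerns the precision of one proportion and makes no allowance for later removals, so it does not bear on the point.

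**2. What happens to a recorded injury.**

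| Event after an injury is recorded | Text that applies | Injury kept? |
|---|---|---|
| Death | Data Collection and Management, plus the three exclusion statements | No, stated |
| Change of care setting | The three exclusion statements, no exception for recorded data | No, by natural reading |
| Discharge before day 7 | Own sentence in the Study Procedure, with a final examination | Probably yes, not stated |

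**3. Effect on the incidence.** The documents give no expected number of injuries or removals. Assume X = 20 injuries in N = 80 patients (25.0%). If k patients are removed, j of them with a recorded injury:

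reported incidence = (X − j)/(N − k)

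| k removed | none injured (j = 0) | all injured (j = k) |
|---|---|---|
| 2 | 20/78 = 25.6% | 18/78 = 23.1% |
| 4 | 20/76 = 26.3% | 16/76 = 21.1% |
| 8 | 20/72 = 27.8% | 12/72 = 16.7% |

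The figure is unchanged when the share injured among those removed equals the overall share; for k = 4 and j = 1 it is 19/76 = 25.0%. Above that share the reported figure is too low, below it too high. For scale, the 95% Wilson interval for 20/80 is 16.8% to 35.5%.

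**4. Effect on the comparison of arms.** Split the same assumed injuries evenly, 10/40 in each arm, so the true difference is zero. Remove 2 patients per arm, both injured in one arm and neither in the other: 8/38 = 21.1% against 10/38 = 26.3%, an apparent difference of 5.3 percentage points. This is the extreme for that removal pattern, not a forecast. It shows that equal numbers of removals do not protect the comparison.

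**5. The proposed rule, worked through.** Take 4 patients with incomplete follow-up, 2 of whom had an injury recorded before leaving. The current plan reports 18/76 = 23.7%. Keeping all randomised patients gives 20/80 = 25.0% if the other 2 are counted as injury-free and 22/80 = 27.5% if they are counted as injured.

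**The case against.** **Only deaths are explicitly discarded.** Correct. For a change of care setting, loss of the record is inferred from exclusion without exception. The inference is natural, but it is one step weaker and is presented here as such.

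**Few patients may be affected.** A reader might infer that every early discharge, or every move from intensive care to the ward, removes a patient. The documents do not support that. Early discharge has its own examination, which would serve little purpose if the patient were then dropped, and the Setting section places the operating room, cardiac intensive care unit and cardiac ward all inside the study. What stands is that the protocol never says outright that discharged patients are retained.

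**No direction is shown.** A reader might infer that the incidence is understated because sicker patients leave. That is plausible, but no figure in the documents shows it, and the ranges above lie on both sides of 25.0%. In the mixed case the shift is 1.3 points (25.0% to 23.7%), well inside sampling error. This limits the claim about size. It does not justify discarding observed outcomes, because a confidence interval does not reveal that loss.

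**The sample is openly described.** This is largely right, and it makes the label of the secondary objective a minor matter. A reader might count the intact-skin requirement as selection bias; it is not, since incidence is defined among people free of the condition at the start. A reader might also take the stated population of 90 against a sample of 80 (89%) as near-complete coverage of the hospital's patients, but that population is not defined, so it settles nothing either way.

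**The duration condition is in the protocol.** It is, in inclusion wording, within the Sample Size calculation section. A reader might infer that its absence from the eligibility lists biases the comparison. It does not, because it applies to both arms alike; it affects only whom the results describe.

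**Sensitivity ranges belong in an analysis plan.** Commonly so, and their absence is not the finding. They are part of the remedy because the present data-use rule would rule them out for patients who die.

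**Conclusion.** The point holds in this form. As written, the protocol discards recorded injuries of patients who die and, on the natural reading, of patients whose care setting changes. This can distort the incidence in the secondary objective and, because removal follows randomisation without blinding, the primary comparison.

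Neither size nor direction can be derived from the documents. Under the assumed 20/80, removing 4 patients moves 25.0% to somewhere between 21.1% and 26.3%, and removing 8 to between 16.7% and 27.8%. If no enrolled patient dies or changes care setting, there is no effect. The fault should be corrected because it is avoidable and touches the primary outcome; it does not by itself invalidate the trial.

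The wide label of the secondary objective and the misplaced over-4-hour condition are real but minor.

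**What to change.** 1. Take the post-enrolment event (death or change of care setting) out of the Exclusion Criteria.
2. Amend the Study Procedure, Data Collection and Management, and Section II so that every randomised patient stays in the denominator and any injury observed before death or transfer is counted, subject to ethics approval of the changed data-use rule.
3. State in the Study Procedure that patients examined at discharge before day 7 are retained, with incomplete follow-up noted where it applies.
4. Report a sensitivity range in which patients with incomplete follow-up and no observed injury are counted first as injury-free and then as injured.
5. Minor: restate the secondary objective as the 7-day incidence among enrolled at-risk trial participants, because it is calculated only from a consenting, Braden-at-risk convenience sample.
6. Minor: reconcile the inclusion and exclusion lists with the over-4-hour condition in the Sample Size calculation section, so that one duration rule governs enrolment.

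**Cost.** A protocol amendment with ethics approval. No new assessments are needed, since the examinations are already scheduled. The secondary claim becomes narrower, and where follow-up is incomplete the result is a range instead of a single percentage.

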### **Objective measures**

#### **For the primary objective**

Pressure ulcer incidence will be assessed by using Bates–Jensen Wound Assessment Tool (BWAT) after operation then day 3 and day 7 for both treatments.

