## **Effectiveness of polyurethane foam dressing compared with Mepilex dressing for pressure ulcer prevention in operating room: A randomized control clinical trial.**

There are two types of intervention available in King Abdullah medical city for operating room pressure ulcer prevention. **Polyurethane foams** (Pink Pad) are a single use system for use in surgical procedures. The system consists of a proprietary formulation for the pink foam pad, non-woven lift sheet, body straps, head rests, and boot liners. It aids hospital facilities in providing a safe and effective method of management of the patient for pressure ulcers and non-movement for patients in the Trendelenburg position.

**Mepilex Border Sacrum** dressings are self-adherent, multilayer foam dressings designed for use on sacrum aiming to prevent pressure ulcers. The dressings are used in addition to standard care protocols for pressure ulcer prevention.

After getting official permission from KAMC IRB, the subject will be randomized using electronic randomization 1:1 ratio. The randomization list was generated electronically through R using the Random Allocation Rule. Patients will equally be allocated into 2 groups randomly. The polyurethane foam group and Mepilex Border Sacrum dressings group.

**Standard PUs preventive care** - All included patients received standard PU prevention according to hospital protocols, based on contextualization and adaptation of International guidelines ( European Pressure Ulcer Advisory Panel, 2021 ), which involved: assessment of PU risk through the Braden Scale at hospital admission, every seven days and when clinically indicated (for example after surgery); full skin assessment during every shift, three times per day combined with routine positioning every 2 h or when required; use of active support surfaces (higher- specification foam mattress or dynamic anti-decubitus mattress) in case of Braden < 16, aiming at preventing damaging tissue deformation and providing an environment that enhances perfusion of at risk tissues; incontinence skin care.

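### Does the primary outcome need a named body site, given the loose description of the pad arm?

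*Protocol*

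**What the plan says.** The primary objective is to compare the two products "in pressure ulcer prevention for patients in operating room". Under Objective measures, "Pressure ulcer incidence will be assessed by using" the Bates-Jensen tool after the operation and on days 3 and 7. Neither place names a site, and neither do the secondary objective and its measure. In Study outcome measurement, Section II is completed when any pressure ulcer occurs. The same paragraph notes that the sacrum is the commonest location, as background.

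The comparator consists of "self-adherent, multilayer foam dressings designed for use on sacrum aiming to prevent pressure ulcers".

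The pad arm is worded in several ways:

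- running title: "Effectiveness of polyurethane foam dressing compared with Mepilex dressing"
- page-footer title: "Effectiveness of polyurethane foam (pink pad) compared with Mepilex dressing"
- Study Procedure, product paragraph: "The system consists of a proprietary formulation for the pink foam pad, non-woven lift sheet, body straps, head rests, and boot liners", with a further purpose of "non-movement for patients in the Trendelenburg position"
- Study Procedure, application paragraph: "polyurethane foam will be used to the patient's sacrum for polyurethane foam group"

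**The concern.** If the pad arm receives the whole system, the arms protect different areas of the body, and an any-site count sets a wider product against a sacral one. If the foam acts only at the sacrum, the arms protect the same area, and ulcers elsewhere dilute the contrast. The introduction treats heels as a relevant site, so non-sacral ulcers are not a remote possibility.

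The trial is open label, and the Blinding section says the outcome assessor cannot be blinded. If the site were truly open, the count could be chosen after results by arm were known, and a conclusion about prevention could rest on the sacrum, on other sites or on a mixture.

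**Working it through.** **1. The plan's own figure.** Sample Size calculation gives a population of 90, expected frequency 50%, error 5% and confidence 99%. Then n0 = 2.576² × 0.5 × 0.5 / 0.05² = 663.5, and n = 663.5 / (1 + 662.5/90) = 79.4. The stated 79 reproduces. It is a precision figure for one proportion and does not depend on the site.

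**2. The outcome passages together.** The primary measure, the secondary measure and the trigger for Section II all speak of pressure ulcers without restriction. The one mention of the sacrum there explains where ulcers usually occur and excludes nothing. An analyst following the text counts a patient with an ulcer at any site.

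**3. The pad passages together.** The objectives, the Introduction, the pilot section and the sample size section all identify the product as polyurethane foam (pink pad). The product paragraph describes what the manufacturer's system contains; the application paragraph describes the study step. A pad that belongs to a larger system can be used at the sacrum, so the two do not contradict each other. What is left unsaid is whether the other components are used. Calling this arm a dressing is loose heading language.

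**4. What the choice of count could do.** The documents give no site-specific rates. Assumptions:

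- any-site risk in the Mepilex arm 29.5% (the Introduction's upper figure, no site stated)
- one site per patient
- sacral share f of 80%, 60% or 50%
- 40 patients per arm

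With risk ratios pad/Mepilex, RR_any = f × RR_sacral + (1 − f) × RR_other. For example, with f = 0.6, RR_sacral = 0.5 and RR_other = 1.0: 0.6 × 0.5 + 0.4 × 1.0 = 0.70.

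Chance that the two observed differences have opposite signs (1,000,000 simulated trials each):

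| RR sacral | RR other | RR any-site (f = 80/60/50%) | Opposite signs |
|---|---|---|---|
| 1.0 | 1.0 | 1.0 / 1.0 / 1.0 | 8 / 15 / 18% |
| 0.5 | 1.0 | 0.60 / 0.70 / 0.75 | 4 / 10 / 13% |
| 1.25 | 0.5 | 1.10 / 0.95 / 0.875 | 8 / 20 / 26% |
| 0.5 | 2.0 | 0.80 / 1.10 / 1.25 | 15 / 43 / 55% |

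The first row is the yardstick. The second lies below it, and the third is level with it or modestly above. Only the fourth clearly exceeds it, and it needs the pad to double ulcers away from the sacrum, which no passage suggests.

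**5. Choosing the better count.** With no effect anywhere, the chance that at least one count is significant at two-sided 5% is 4.3/4.7/4.7% with Fisher's test and 7.3/8.3/8.8% with Pearson's chi-square. The protocol names no test.

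**6. Would a sacral outcome gain power?** For RR_sacral = 0.5, exact Fisher power is 20/13/10% for the sacral count. The any-site count gives 27/27/27% if RR_other = 0.5 and 17/10/8% if RR_other = 1.0. Neither count is better throughout.

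**The case for a change.** The strongest case for acting is that the event defining the primary outcome, and what each arm receives, belong in the protocol. One sentence would settle both. The remark that the sacrum is commonest, together with foam placed at the sacrum and a sacral comparator, lets a reader infer a sacral outcome with some reason.

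A true reversal is also arithmetically possible without the doubling scenario. Take independent sites, sacral rates of 10% (Mepilex) and 15% (pad), and non-sacral rates of 15% and 5%. The sacral difference is +5 points. The any-site rates are 1 − 0.90 × 0.85 = 23.5% and 1 − 0.85 × 0.95 = 19.25%, a difference of −4.25 points. Opposite signs then occur in about 34% of simulated trials, against 14–17% under that model with no true difference.

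The arithmetic stands, and so does the point that the wording is loose. But this reversal needs a pad that is worse at the sacrum and much better elsewhere, on rates the protocol does not supply. Even then the any-site result is not wrong: it reports correctly that fewer patients on the pad developed an ulcer, which is what the stated objective asks. The unblinded assessor is a separate limitation that naming a site would not remove.

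**Conclusion.** No change is needed. This is a gap in detail with a sensible default. Read as written, the outcome and recording passages give an any-site count, made in the same way in both randomised arms. If the pad covers more of the body, that count includes its wider effect. If it acts only at the sacrum, the true effect is diluted (0.5 becomes 0.60 to 0.75 under the assumed shares) but not reversed. A sacral outcome would also be defensible, so the concern shows no error in the one the text implies.

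Most of the apparent disagreement between the counts is what 40 patients per arm produce by chance. Selection between them matters only moderately: under 5% with Fisher's test, up to about 9% with Pearson's chi-square. These sizes depend on the 29.5% risk, the 50–80% sacral shares, the chosen ratios and one site per patient, none of which the protocol establishes for this comparison. The data form is not shown and may already record the site of each injury. On which pad components are used, the wording is loose, and this review takes no position.
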